Through supplemental funding, the study team will also test the central hypothesis that climate change-induced disruptions in air quality worsen asthma inflammation, symptoms, and longitudinal outcomes in school-age children with asthma and that these effects are mediated by social vulnerability. Two additional aims to be pursued are below:

**Aim 4. Determine associations between climate, air quality, symptoms, and outcomes in children with exacerbation-prone asthma during two climate seasons.**

Hypothesis: Children with greatest social vulnerability will have more air pollution exposure, increased symptoms, poorer lung function, more exacerbations and decreased QOL during each season.

**Aim 5. Determine the biological impact of climate and pollutants in children with exacerbation prone asthma.** Children with greatest social vulnerability and the highest air pollution exposure will have differentially expressed cytokines and metabolomic features.

This project involves a multidisciplinary team with a history of collaboration and is aligned with the NINR Strategic Plan to “*Advance Symptom Science Research*” in chronic conditions through biobehavioral research. The study population, children with exacerbation-prone asthma, has also been understudied in this regard. This project is expected to: 1) refine knowledge regarding the identification and clinical utility of symptom clusters in these children, and 2) identify mechanisms underlying symptom clusters that can be targeted in future interventional studies, to reduce the high morbidity and improve quality of life.

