The secondary outcome, quality of life, will be compared with generalized estimating equations at visits 3, 4 and 5 using latent class assignment as the predictor. Analyses will be evaluated in light of pertinent covariates such as age, sex, race, ethnicity, socioeconomic status, medications, exposures and allergic sensitization. A 0.05 significance threshold will be utilized for secondary analyses without adjustment for multiple comparisons.

Metabolomic data, cytokine data, and amino acid data will be quantitative, linear mixed effects models will be used to determine the association between these symptom cluster group assignment.

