### **Plan for supplemental R01 funding (aims 4-5)**

Aim 4 will determine associations between neighborhood air quality indices (predictor variables) and patient-reported asthma control and symptoms, lung function, exacerbation rates and QOL (outcome variables) during two separate seasons (spring/summer versus fall/winter) in children stratified by high- versus low-to-moderate social vulnerability. Prespecified outcomes are continuous and will be evaluated with linear regression. Analyses will be stratified by social

vulnerability (high versus low-to-intermediate) and season (spring/summer versus fall/winter). Models will be generated for air quality variables on the visit date and for each of the five lag days prior to the visit. Given the relatively small number of participants and high number of air quality predictor variables, we will use ElasticNet to select the most important variables in Python. Variables with a Pearson correlation coefficient  $>0.8$  will be removed to minimize redundancy. Models will be evaluated considering pertinent covariates such as age, asthma medications and tobacco smoke exposure. To further address sex as a biological variable, models will also be fitted by sex, with statistical comparison of results observed in boys and girls. Analyses will assume a type 1 error rate of 0.05 without adjustments for multiple testing (exploratory study). For exploratory dichotomized outcomes that are not pre-specified, such as exacerbation occurrence or QOL scores below a threshold, partial least squares regression and discriminant analysis could be performed to determine the air quality features that provide the largest separation between outcomes. Temporal stability of the results would be assessed by repeating analyses during the second season.

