Aim 5 will determine whether children with greatest social vulnerability and the highest air pollution exposure will have differentially expressed cytokines and metabolomic features. Cytokine and metabolomics data will be integrated using the R package Multiple Co-inertia (MCIA) to identify novel biomarkers of climate-related outcomes. These co-inertial analyses (CIA) are similar to the sparse Partial Least Squares (sPLS) approach used to integrate multi-omics data in the analyses pipeline from the popular package mixOmics by maximizing the covariance between eigenvectors and efficiently determining key features driving variance in paired multi-omics samples. Unlike sPLS, CIA allows us to project multi-omic data in the same space, reducing the need to generate several paired multi-omic integration modules.

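### Aim 5 asks whether biomarkers differ by pollution exposure and social vulnerability, but its only stated analysis includes neither variable and no stated step links its output to them

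*Combined protocol and SAP*

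**What the plan says.** Section B states the Aim 5 hypothesis: "Children with greatest social vulnerability and the highest air pollution exposure will have differentially expressed cytokines and metabolomic features". Section U, under the plan for aims 4-5, repeats it as the question to be answered: "Aim 5 will determine whether children with greatest social vulnerability and the highest air pollution exposure will have differentially expressed cytokines and metabolomic features".

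The method follows directly: "Cytokine and metabolomics data will be integrated using the R package Multiple Co-inertia (MCIA) to identify novel biomarkers of climate-related outcomes". The plan describes how the method works: "maximizing the covariance between eigenvectors and efficiently determining key features driving variance in paired multi-omics samples". The rest of the Aim 5 paragraph compares co-inertia with sparse partial least squares as a way of integrating assays. It gives no exposure metric or window, vulnerability group, covariate, choice of visit, estimate or test.

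**The concern.** The hypothesis concerns two variables measured outside the laboratory, pollution exposure and social vulnerability. The analysis takes in two laboratory tables and looks for what they have in common. The strongest shared variation need not be related to exposure. The protocol itself contains other plausible sources of it: ages from 6 up to 21, blood taken without fasting (Section R), and samples from before and after triamcinolone at visits 1 and 2 (Section K), with no statement of which visit Aim 5 uses.

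At stake is the label put on the result. Features with high loadings could be reported as biomarkers of climate-related outcomes although no step has related them to climate, pollution or vulnerability. The hypothesis would be neither supported nor refuted.

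**Working it through.** The plan gives no sample size, power or effect size for Aim 5, so there is no figure to reproduce. The check is a reading of every place that could supply the missing model, followed by an illustration.

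**Step 1. Could another part of Section U supply the model?**
- *Aim 4 paragraph.* Its regressions use air quality as predictor, but the listed outcomes are "patient-reported asthma control and symptoms, lung function, exacerbation rates and QOL (outcome variables". No cytokine or metabolite is among them. The stratification by "vulnerability (high versus low-to-intermediate) and season (spring/summer versus fall/winter" is stated for those regressions. The optional discriminant analysis separates dichotomised clinical outcomes by air quality features.
- *Plan for aims 1-3.* Cytokines and metabolites are modelled here: "linear mixed effects models will be used to determine the association between these symptom cluster group assignment". The predictor is symptom cluster, not exposure or vulnerability.
- *Aim 5 paragraph.* Co-inertia of the two assay tables only.

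None of the three relates a cytokine or metabolite to exposure or vulnerability.

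**Step 2. What could the leading features look like?** Two-table co-inertia was computed as the singular value decomposition of the cross-covariance of the standardised tables. Everything here is assumed: 147 children (the parent study's number after attrition, since none is given for Aim 5), one quarter of them in the high-vulnerability, high-exposure group, and the panel sizes, shifts and shared factors below. The shared factors are unrelated to the group.

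| Set-up | Truly shifted share of top features | Expected by chance |
|---|---|---|
| 100 cytokines, 300 metabolites; 10 per table shifted 0.8 SD; two shared factors; 200 runs | 9% of top 10 cytokines on axis 1 | 10/100 = 10% |
| 60 cytokines, 300 metabolites; 5% shifted; two shared factors; 300 runs per effect size | 4.4% (0.6 SD), 4.2% (0.8 SD) of top 20 on axes 1-2 | 5% |
| Same panels; three strengths of shared factor; 100 runs each | 1.5-4% of top 20 | 5% |
| Same panels; no shared factors; 100 runs each | 8% (0.6 SD), 17% (0.8 SD) of top 20 | 5% |
| Same panels; no shared factors; 20% shifted by 0.8 SD; 150 runs | 68% of top 20 | 20% |

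In the first set-up the mean absolute correlation of axis 1 with the group label was 0.07.

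**Step 3. Does the output carry the contrast if someone tests for it?** With two shared factors and 5% of features shifted, the first five co-inertia scores were compared between groups, and a difference was declared if any score had p<0.01. It was found in 52% (0.6 SD) and 75% (0.8 SD) of 150 runs, and in 8% with no effect (nominal: 1 - 0.99^5 = 0.049). Over the settings tried, detection at 0.8 SD was 73-100%.

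**Step 4. What does a supervised test find?** Two-group t-tests per feature with Benjamini-Hochberg control found 34% (0.6 SD) and 72% (0.8 SD) of the shifted features at 4.8% false discovery. A second set of runs gave 42-45% and 84-85% at 3-5%. Further runs with shared factors and 5% of features shifted gave 16-44%. The spread reflects the assumed noise.

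**Step 5. What if the Aim 4 error rule were used per feature?** Expected false positives = number of null features x 0.05. Section D describes up to 100 multiplexed biomolecules and hundreds of small molecules. With 400 null features (assumed): 400 x 0.05 = 20. Over a range of 100 to 1,000 features: 5 to 50.

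**The case against.** Three points can be made for the plan.

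**Co-inertia may be only the integration step.** The paragraph is a short sketch that opens with the contrast, and the method yields scores and loadings that can be compared between groups, or exposure could be added as a further table. This stands as a limit. A reader might infer that the planned method cannot test the hypothesis, or that its features would be no better than chance. The documents do not support either reading: they leave the linking step unstated, and Step 3 shows that scores can carry the contrast. The near-chance results come from set-ups with two strong shared factors and an inspection of only the first one or two axes, which those factors occupy. It remains true that neither form of follow-up is written down.

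**The Aim 4 rules may be shared.** A reader might also infer that no error rule exists for Aim 5. The heading covers both aims, and beneath it stands: "Analyses will assume a type 1 error rate of 0.05 without adjustments for multiple testing (exploratory study". The exploratory status and the vulnerability strata may well be meant for both. That would give Aim 5 an error rate and a grouping, but still no model, because the paragraph opens with Aim 4 and lists clinical outcomes.

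**The remedy is one choice among several.** Comparing co-inertia scores between groups, or a supervised sparse partial least squares model, would also address the question. The sensitivities in Step 4 come from comparing one combined group with the rest. A model with a product term would generally be less sensitive, so they must not be read as its power.

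**Conclusion.** The point holds as a gap in the written plan: Aim 5 poses a contrast by exposure and vulnerability, and no stated analysis estimates or tests it. That rests on the text alone.

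The size of the consequence is uncertain. The truly related share of the 20 leading features ran from about chance level to about two thirds, depending on how much unrelated variation the assays share and how many features exposure shifts. The documents give neither, so no single figure should be presented as the expected performance of the plan.

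This should be fixed but is not critical. Aim 5 came in with the supplement in Version 5, and the supplement's analyses are described as exploratory. The ACQ response, the PAIS outcome and the sample size do not depend on it. An exploratory label can justify relaxed error control; it does not replace the two variables the hypothesis is about.

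**What to change.** Add a supervised step to the Aim 5 paragraph of Section U:

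- Model each cytokine and metabolomic feature, and the first few co-inertia scores, on air pollution exposure and social vulnerability. Include their joint effect, or compare a pre-defined high-vulnerability, high-exposure group with the rest.
- Name the exposure metric and time window, the vulnerability measure and its cut-point, and the number of scores to be examined.
- Use visit 1 samples, taken before the injection. Both follow-up options collect them, so all participants can contribute.
- Adjust for age, asthma medications and tobacco smoke exposure, the covariates already named for Aim 4.
- Control the false discovery rate across features, for example at 5%.
- Keep co-inertia as a descriptive analysis, and base any claim of a climate-related biomarker on the supervised results.

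The cost is SAP wording and a little more analysis; the assays and samples are already planned. The downside is that fewer features will be named, since false-discovery control is stricter than an unadjusted 0.05, and a joint-effect term will be estimated with limited precision at this sample size.

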## V. Timeline

	Pre-award	Year 1 first 3 months	Year 1 last 9 months	Year 2	Year 3	Year 4	Year 5
Start-up activities							
Institutional Review Board approval	X						
Georgia CTSA study approval (for utilization of the Pediatric Research Center)	X						
Develop study case report forms		X					
Develop study database		X					
Develop participant characterization Manual of Procedures		X					
Develop laboratory sample processing Manual of procedures		X					
Study team training		X					
Participant-related activities							
Creation of advertisements, mailings		X					
Screening and recruitment	X	X	X	X	X		
Participant enrollment		X	X	X	X		
Participant follow-up (48 week study)		X	X	X	X	X	X
Laboratory procedures							

Cytokine analyses			X	X	X	X	X
Metabolomic analyses			X	X	X	X	X
Statistical analyses							
Preliminary analyses for progress reporting						X	
Primary/secondary outcome analyses							X
Dissemination							
Research conference presentation						X	X
Manuscript development					X	X	X
Grant submission							
Future related studies							X



**Appendix I. Schedule of study procedures for the 48 week cohort study (option 2).  
Procedures that will not be performed if telephone follow-up visits are requested are indicated by an (X).**

6-21 years with diagnosed asthma and an asthma exacerbation in the past 12 months		Visit (week) (window)	Visit 1* (2) (+7 days)	Visit 2 (16) (+4 weeks)	Visit 3 (32) (+4 weeks)	Visit 4 (48) (+4 weeks)	Visit 5
		Baseline	Steroid response	Follow-up	Follow-up	Follow-up	
Procedure							
	Consent		X				
Eligibility	Vital signs, physical exam	X	X	(X)	(X)	(X)	
	Medical history review	X	X	X	X	X	
	Urine pregnancy testing	X	X	(X)	(X)	(X)	
Characterization	Demographic questionnaires	X					
	Asthma evaluation (ACQ/ ACT)	X	X	X	X	X	
	PROMIS questionnaires	X	X	X	X	X	
	Spirometry	X	X	(X)	(X)	(X)	
	• Bronchodilator reversibility	X	X			(X)	
Mechanisms	Exhaled nitric oxide	X	X	(X)	(X)	(X)	
	Venipuncture	X	X			(X)	
	• Total IgE, specific IgE	X					
	• Complete blood count/diff	X	X			(X)	
	• Blood samples stored (aim 3)	X	X			(X)	
	Sputum induction	X	X			(X)	
	• Sputum sample stored (aim 3)	X	X			(X)	
	Triamcinolone injection	X					

\* Can be split into two visits (V1A and V1B, with triamcinolone at V1B)
